6.1.2. Statistical Hypothesis for the Primary Efficacy Endpoint

Null hypothesis: The RDV groups are not different from the PTM groups in virologic response with respect to DAVG₇ in SARS-CoV-2 viral load.

Alternative hypothesis: The RDV groups are different from the PTM groups in virologic response with respect to DAVG₇ in SARS-CoV-2 viral load.

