8.5. Efficacy Analysis

8.5.1. Primary Analysis

SARS-CoV-2 viral load will be summarized by treatment using descriptive statistics in Part A and Part B. For Part C, time weighted average change in SARS-CoV-2 viral load will be compared between the RDV and placebo groups using analysis of covariance with baseline viral load included in the model as a covariate.

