3.2. Participant Grouping

For analyses based on the All Randomized Analysis Set, FAS, or mFAS, participants will be grouped according to the treatment to which they were randomized. For analyses based on the Safety Analysis Set, participants will be grouped according to the actual treatment received. The actual treatment received will differ from the randomized treatment only when their actual treatment differs from randomized treatment for the entire treatment duration. For the PK Analysis Set, participants will be grouped according to the actual treatment received.

The analysis of time-weighted average change from baseline through day 7 (DAVG7) in SARS-CoV-2 viral load based on the mFAS, and time to COVID-19-related MAVs or all-cause death by Day 28 based on the FAS may also be grouped according to the following:

- 5 RDV treatments (31 mg for 3 days vs. 31 mg for 5 days vs. 62 mg for 3 days vs. 62 mg for 5 days vs. 39 mg for 5 days) vs. pooled PTM (Parts A, B, and C)
- Pooled all RDV treatments (31 mg for 3 days, 31 mg for 5 days, 62 mg for 3 days, 62 mg for 5 days, and 39 mg for 5 days) vs. pooled PTM (Parts A, B, and C)
- Pooled 31 mg RDV (31 mg for 3 days and 31 mg for 5 days) vs. pooled 62 mg RDV (62 mg for 3 days and 62 mg for 5 days) vs. 39 mg RDV for 5 days vs. pooled PTM (Parts A, B, and C)

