3.5. Multiple Comparisons

No prespecified multiplicity adjustments are planned for confidence intervals or statistical tests.

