6.1.3. Analysis of the Primary Efficacy Endpoint

DAVG₇ in SARS-CoV-2 viral load will be summarized by treatment group using descriptive statistics in Parts A, B and C. For Part C, DAVG₇ in SARS-CoV-2 viral load will be compared between the RDV and PTM groups using analysis of covariance (ANCOVA) with baseline viral load included in the model as a covariate. Due to small sample sized in Parts A and B, no comparison test will be applied.

The following summary tables will be provided by treatment group:

- DAVG₇ in SARS-CoV-2 viral load based on nasopharyngeal swab samples
- DAVG₇ in SARS-CoV-2 viral load based on oropharyngeal swab samples
- DAVG₇ in SARS-CoV-2 viral load based on saliva samples

After checking that the Part A, Part B, and Part C data are poolable with regard to demographic and baseline characteristics, DAVG₇ in SARS-CoV-2 viral load will be analyzed by the pooled groups outlined in Section 3.2 and comparison will be done using ANCOVA with baseline viral load as the covariate.

The mFAS will be the primary analysis set for evaluation of DAVG₇ in SARS-CoV-2 viral load. A by-participant listing for DAVG₇ in SARS-CoV-2 viral load will be provided. Descriptive statistics will be provided for DAVG₇ in SARS-CoV-2 viral load by treatment group for each of the subgroups defined in Section 3.4.

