	Total Bilirubin	Increase	Total Bilirubin (Hyperbilirubinemia)
	Uric Acid	Increase	Uric Acid (Hyperuricemia)
	Prothrombin Intl. Normalized Ratio (INR)	Increase	Prothrombin Intl. Normalized Ratio (Increased)
	Activated partial thromboplastin time (aPTT)	Increase	Activated partial thromboplastin time (Increased)
	Prothrombin Time (PT)	Increase	N/A

17) The first Part B participant was screened on Oct 29, 2020 and the first Part C participant was screened on Jan 24, 2021. Screen failure participants of each study part is derived from scrndt,

```
if part=" then do;  
  if .< scrndt <29Oct2020 then part='Part A';  
  else if scrndt >= 29Oct2020 & scrndt <24Jan2021 then part='Part B';  
  else part='Part C';  
end;
```

18) SARS-CoV-2 viral load from nasopharyngeal and oropharyngeal swabs and saliva samples were to be collected. SARS-CoV-2 viral load in nasopharyngeal and oropharyngeal swabs and saliva samples will be analyzed separately.

- a) For numeric SARS-CoV2 summary (e.g, mean viral load, change from baseline etc.), “Inconclusive” SARS-CoV2 result is set to missing.
- b) For categorical SARS-CoV2 summary, 3 categories will be included, i.e. Positive, Inconclusive, and Negative.
 - i) Positive = any numeric result or “<LLOQ SARS-CoV2 detected” - LLOQ could vary by sample type
 - ii) Negative = “No SARS-CoV2 detected”
 - iii) Inconclusive = “Inconclusive”
- c) For Negative SARS-CoV2 confirmation, “Inconclusive” SARS-CoV2 result will not be considered as missing thus a “Negative” followed by a “Inconclusive” is NOT confirmed.
- d) 2 negative results from the same day do not equal confirmation.
- e) If last PCR sample is negative for participants completed the study or for participant withdrawn early from the study, then one negative PCR of last sample is considered as confirmed negative.
- f) Categorical SARS-CoV2 and SARS-CoV2 negative summary will be separated out by sample type. There will be no combined positive or negative category using 2 or more sample types.

19) SAS code for ANCOVA analysis of DAVG:

```
ods output ParameterEstimates=out1 LSMeans=out2 LSMeanCL=out3  
LSMeanDiffCL=out4;  
proc glm data=dat1 plots=none;  
  class trt01pn;  
  model DAVG = trt01pn base / solution;  
  lsmeans trt01pn / stderr cl pdiff;  
run;  
ods output close; quit;
```

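### SAP 6.1.2 does not tie the primary hypothesis to the Part C comparison that the protocol names, and SAP 6.1.3 adds unranked, unadjusted pooled comparisons under the same heading

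*SAP*

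**What the plan says.** Protocol 8.5.1, headed Primary Analysis, describes viral load in Parts A and B and makes one comparison: "For Part C, time weighted average change in SARS-CoV-2 viral load will be compared between the RDV and placebo groups", by ANCOVA with baseline viral load as covariate. It contains no pooled analysis.

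SAP 6.1.2 states the null as "The RDV groups are not different from the PTM groups in virologic response" and the alternative as "Alternative hypothesis: The RDV groups are different from the PTM groups in virologic response", with respect to DAVG7. Neither sentence names a Part or a treatment group.

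SAP 6.1.3 says that DAVG7 in Part C "will be compared between the RDV and PTM groups using analysis of covariance (ANCOVA") with baseline as covariate, and that Parts A and B are not tested. It then says that, once the Parts have been checked as poolable on demographic and baseline characteristics, the groupings of SAP 3.2 are analysed and "comparison will be done using ANCOVA with baseline viral load as the covariate".

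SAP 3.2 lists three groupings, all against placebo pooled over Parts A, B and C: the five RDV regimens separately, all RDV together, and RDV by dose (31, 62, 39 mg). Here the status is optional: participants "may also be grouped according to the following".

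SAP 3.5 says "No prespecified multiplicity adjustments are planned for confidence intervals or statistical tests". The ANCOVA code in SAP Appendix 2, item 19, fits treatment and baseline only, and requests "lsmeans trt01pn / stderr cl pdiff" with no control group named.

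**The concern.** A plan that writes a null and an alternative hypothesis should say which test answers them. Here the hypothesis speaks of groups without naming them, and the section that analyses the primary endpoint offers the Part C test and then the pooled tests. The pooled tests are optional in SAP 3.2 and stated as to be done in SAP 6.1.3. Their only gate is a poolability check that names the characteristics to compare but gives no threshold.

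If the Part C test and the all-RDV pooled test gave different verdicts, the SAP does not say which one answers 6.1.2. Protocol 5.1.2 makes the study sponsor-unblinded, with access for certain staff limited to need. SAP v1.0 was signed on 7 June 2021, after Part C screening began on 24 January 2021 (SAP Appendix 2, item 17). Nothing in the documents suggests that a choice was made on results, but the plan leaves room for it. Protocol 1.3 says that Part C, with a further Phase 1a cohort, will inform Phase 3 dose selection, so it matters which result is presented as primary.

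**Working it through.** **Inputs from the documents.** Parts A and B: 36 each, 1:1:1, so 12 per arm. Part C: 80, 3:1, so 60 RDV and 20 placebo. The stated total is reproduced: 36 + 36 + 80 = 152. Pooled RDV is 4 × 12 + 60 = 108; pooled placebo is 12 + 12 + 20 = 44.

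**Assumptions.** The plan gives no alpha, SD, effect size or power for DAVG7. I take two-sided 5%, residual SD = 1 after baseline adjustment, no dropout or mFAS exclusions, and one specimen type.

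**Counting the contrasts.** Item 19 prints all pairs: 15 in the six-group model, 6 in the four-group model, 1 for all RDV versus placebo and 1 in Part C, which makes 23. Of these, 10 + 3 = 13 compare RDV with RDV. That leaves 10 RDV-versus-placebo p-values. The contrast of 39 mg with pooled placebo appears in two models, so 9 are distinct.

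**Precision.** SE = √(1/n₁ + 1/n₂); effect detectable with 80% power = (1.96 + 0.84) × SE.

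| Contrast | n | SE (SD units) | Detectable effect |
|---|---|---|---|
| Part C | 60 v 20 | 0.258 | 0.72 SD |
| All RDV v pooled placebo | 108 v 44 | 0.179 | 0.50 SD |
| 39 mg v pooled placebo | 60 v 44 | 0.198 | 0.56 SD |

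**False-positive rate, no Part effect.** The Part C and all-RDV estimates share participants. Their covariance is 1/108 + 1/44, so their correlation is 0.179/0.258 = 0.69. With that correlation, the chance that at least one of the two tests is significant under the null is 8.4%. For any of the nine distinct contrasts it is about 25% by simulation; if they were independent it would be 1 − 0.95⁹ = 37%.

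**Disagreement between the Part C and all-RDV verdicts.** From 40,000 simulated trials per scenario using the SAP's ANCOVA, with the same effect in every RDV arm:

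| True effect | Verdicts differ | Pooled only significant | Part C only significant |
|---|---|---|---|
| 0 | about 7% | about 3% | about 3% |
| 0.3 SD | 26% | 22% | 4% |
| 0.5 SD | 36% | 34% | 2% |
| 0.7 SD | 22% | 22% | under 1% |
| 0.9 SD | 7% | 7% | 0% |

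A normal approximation with correlation 0.69 gives 7%, 26%, 35%, 21% and 6%. At 0.5 SD, simulated power is 48% for Part C and 80% for all RDV.

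**What the missing Part term does.** The 39 mg arm lies wholly in Part C, but 24 of the 44 pooled placebo participants come from Parts A and B. If Part C differs from A and B by s for reasons other than drug, the contrast is biased by s × 24/44:

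- s = 0.3 SD: bias 0.164, or 0.164/0.198 = 0.82 SE; rejection rate about 13%.
- s = 0.5 SD: bias 0.273, or 1.37 SE; about 28% by this approximation and 27% in simulation.

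The Part C test stays at 5% in both cases.

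A Part difference is plausible from the plan itself. DAVG7 starts at the first post-baseline value (SAP 6.1.1). Swabs fall on Days 2 to 5 and 7 in Parts A and B, but on Days 3, 5 and 7 in Part C. With an assumed steady fall of 0.3 log₁₀ per day, DAVG7 is −0.3 × (4.5 − 1) = −1.05 in A and B, and −0.3 × (5 − 1) = −1.20 in C, with no drug effect. A check on demographic and baseline characteristics cannot see this. For the pooled COVID-19-related MAV summary, SAP 6.2.1 does stratify by Part.

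**The case against.** The strongest reply is that the primary contrast is already identifiable. Protocol 8.5.1 tests only Part C. SAP 6.1.3 gives that test first and without conditions, rules out tests within Parts A and B, and makes the pooled tests conditional. This stands: a reader might infer that no single contrast decides the trial, and the documents do not support that. The fault is that 6.1.2 is not tied to the contrast the protocol names.

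A reader might also infer from the plural in 6.1.2 that the all-RDV contrast is the one meant. That is only one reading, because both documents use the plural for the two-arm Part C comparison as well. The protocol synopsis adds a third wording, each RDV group compared with placebo. That adds to the ambiguity, but it also means regimen-level comparisons are not purely a SAP invention.

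Third, the study is early-phase with a descriptive aim, no power calculation and no success rule, and both documents state openly that multiplicity is not adjusted. This stands, and it limits the seriousness of the point. It does not remove the need to say which test answers a stated hypothesis.

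Finally, most of the disagreement at 0.3 to 0.7 SD is the larger sample finding a real effect that Part C misses. That is correct: the figures describe a difference in power and do not show that the pooled result misleads.

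**Conclusion.** The point holds as a gap in specification that should be closed. The SAP hypothesis is not linked to the Part C ANCOVA of Protocol 8.5.1, and the pooled comparisons sit beside it under the primary-endpoint heading without rank, label or adjustment. Naming Part C holds the primary test at 5%, against about 8.4% if either of the two main contrasts could be claimed and about 25% across the nine distinct ones.

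Two stronger readings should be avoided. Counting all 23 printed p-values gives a false-positive rate near 40%, but 13 of them compare RDV with RDV and cannot test RDV against placebo. Nor can one say in general that the contrasts often disagree: the 22% to 36% range needs a common true effect of 0.3 to 0.7 SD, and it falls to about 7% at zero or 0.9 SD.

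All figures rest on the assumed 5% level, SD units, planned arm sizes and one specimen type. Exclusions from the mFAS would lower power.

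**What to change.** 1. Reword SAP 6.1.2: in Part C, baseline-adjusted mean DAVG7 does not differ between Group 7 (39 mg) and Group 8 (PTM), two-sided 5%. State that this is the only test of the primary hypothesis.
2. In SAP 3.2 and 6.1.3, label the pooled analyses supportive, and use the same term in both sections for whether they will be done. Report adjusted differences with 95% CIs, limited to RDV-versus-placebo contrasts.
3. Add Part to the class and model statements of item 19 for the pooled analyses.

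The third change costs almost nothing for the all-RDV contrast. The within-Part information, n₁n₂/(n₁ + n₂), is 24 × 12/36 = 8 in each of A and B and 60 × 20/80 = 15 in C. The total is 31, against 108 × 44/152 = 31.3 without Part, so the detectable effect stays at 0.50 SD. In the by-dose and by-regimen models each RDV arm occurs in one Part only. With Part included, each is compared in effect with its own Part's placebo, and pooling then helps only through the shared residual variance and baseline slope. That is the price of removing the 13% to 27% error shown above.

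The other downside is small: the more powerful pooled contrast can no longer be presented as the primary result. Dropping p-values from the pooled tables, testing the pooled contrast only after Part C is significant, or a Dunnett adjustment are optional in a study of this kind. No new data are needed.

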6.1.3. Analysis of the Primary Efficacy Endpoint

DAVG₇ in SARS-CoV-2 viral load will be summarized by treatment group using descriptive statistics in Parts A, B and C. For Part C, DAVG₇ in SARS-CoV-2 viral load will be compared between the RDV and PTM groups using analysis of covariance (ANCOVA) with baseline viral load included in the model as a covariate. Due to small sample sized in Parts A and B, no comparison test will be applied.

The following summary tables will be provided by treatment group:

- DAVG₇ in SARS-CoV-2 viral load based on nasopharyngeal swab samples
- DAVG₇ in SARS-CoV-2 viral load based on oropharyngeal swab samples
- DAVG₇ in SARS-CoV-2 viral load based on saliva samples

After checking that the Part A, Part B, and Part C data are poolable with regard to demographic and baseline characteristics, DAVG₇ in SARS-CoV-2 viral load will be analyzed by the pooled groups outlined in Section 3.2 and comparison will be done using ANCOVA with baseline viral load as the covariate.

The mFAS will be the primary analysis set for evaluation of DAVG₇ in SARS-CoV-2 viral load. A by-participant listing for DAVG₇ in SARS-CoV-2 viral load will be provided. Descriptive statistics will be provided for DAVG₇ in SARS-CoV-2 viral load by treatment group for each of the subgroups defined in Section 3.4.

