Part C: 39 mg (nominal dose) by mouthpiece of Remdesivir for Inhalation Solution formulation administered via inhalation once daily at approximately the same time each day

Reference Therapy, Dose, and Mode of Administration:

Placebo administered via inhalation once daily at approximately the same time each day

Criteria for Evaluation:

Safety: Proportion of participants with treatment-emergent AEs and laboratory abnormalities.

Efficacy:	Change in SARS-CoV-2 viral load will be measured. A FLU-PRO [®] questionnaire will be utilized to report COVID-19 symptom severity and duration. Disease progression from baseline will be assessed by duration and change in severity of COVID-19 clinical symptoms and need for medically attended visits (MAVs).
Pharmacokinetics:	For Parts A and B, the plasma concentrations of inhaled RDV and its metabolites will be measured, as appropriate. The following plasma PK parameters will be calculated for each analyte (RDV, GS-441524 and GS-704277), as applicable: AUC _{0-24h} , AUC _{tau} , AUC _{last} , CL _{SS/F} , t _{1/2} , V _{Z/F} , C _{max} , T _{max} , C _{last} , T _{last} , λ _Z , C _{tau} . CCI
Statistical Methods:	
No statistical sample size/power calculation was performed as the sample size of up to approximately 152 participants is deemed feasible and sufficient to provide a descriptive assessment of viral kinetics, safety and tolerability, PK and disease progression in this study.
 
Antiviral activity evaluation will be based on time weighted average change in SARS-CoV-2 viral load (defined as the AUC of viral load change divided by time between baseline to Day 7) and will be summarized by treatment group and each RDV group compared with placebo.

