8.5.2. Secondary Analyses

The proportion of participants all-cause MAV (medical visits attended in person by the participant and a health care professional) or death by Day 28 will be estimated using Kaplan-Meier methods by treatment group in Part C. The proportion of participants COVID-19 related MAVs or death by Day 28 will be estimated using Kaplan-Meier methods by treatment group in Part C. The proportion of hospitalization by Day 28 will be summarized by treatment group. Kaplan Meier product limit method will be used to estimate time to negative SARS-CoV-2 PCR and time to alleviation (mild or absent) of baseline COVID-19 symptoms by treatment group.

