6.2.1. Analysis of Secondary Efficacy Endpoints

The FAS will be the primary analysis set for hospitalizations, MAVs and FLU-PRO questionnaire analyses. The mFAS will be the primary analysis set for SARS-CoV-2 viral load analyses.

Composite Endpoint of All-Cause MAVs or All-Cause Death by Day 28

The proportion of participants with all-cause MAVs or all-cause death by Study Day 28 will be estimated using Kaplan-Meier methods by treatment group and compared among 3 treatment groups in Part A and Part B and between the 2 treatment groups in Part C using a log-rank test.

If participants have no event by Study Day 28, participants will be censored at date of earlier of Study Day 28 and last study day. If a participant has a MAV first and then dies, then date of the MAV and status will be used for this participant.

Composite Endpoint of COVID-19 Related MAVs or All-Cause Death by Day 28

The proportion of participants with COVIS-19 related MAVs or all-cause death will be analyzed using the same method as used for composite endpoint of all MAVs or all-cause death by day 28.

In addition, a summary by pooled RDV and Pooled PTM may be provided and compared using CMH method including Part as strata in the model.

Proportion of participants hospitalized by Day 28

The proportion of participants with all-cause hospitalization (ICU, non-ICU, or unknown ward from Hospitalization/MAVs CRF) by Study Day 28 will be estimated using the Kaplan-Meier method and compared among treatment groups using a log-rank test. The time to all-cause hospitalization is defined using the first hospitalization date by Study Day 28, depending on which happens first. If participants have no event by Study Day 28, participants will be censored at date of earlier of Study Day 28 and last study day/death.

Time to Negative SARS-CoV-2 PCR

Negative SARS-CoV-2 PCR based on RT-PCR viral load is defined as:

- (1) the results reported as ‘No SARS-CoV-2 detected’, AND
- (2) two consecutive negative results, or negative at last available sample for participants who completed or discontinued from study.

The time to negative SARS-CoV-2 PCR is defined (in days) as the number of days to first confirmed negative:

First date of two consecutive dates achieving negative result – First dose date +1.

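### No baseline-adjusted within-Part difference with a confidence interval is planned on DAVG7 for the 31 mg and 62 mg regimens, although the synopsis says each RDV group is compared with placebo

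*SAP*

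**What the plan says.** Five places bear on how the 31 mg and 62 mg regimens are set against placebo on viral load.

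- **Protocol synopsis, Statistical Methods.** DAVG7 "will be summarized by treatment group and each RDV group compared with placebo". No Part is singled out.
- **Protocol 8.5.1.** "SARS-CoV-2 viral load will be summarized by treatment using descriptive statistics in Part A and Part B". ANCOVA with baseline viral load is named for Part C only.
- **SAP 6.1.2.** The null hypothesis is general: "The RDV groups are not different from the PTM groups in virologic response". It is not limited to Part C.
- **SAP 6.1.3.** DAVG7 is summarized by treatment group in all Parts, and ANCOVA is run in Part C. For the other two Parts: "Due to small sample sized in Parts A and B, no comparison test will be applied". A pooled ANCOVA follows if the Parts are found poolable on demographic and baseline characteristics.
- **SAP 3.2 and Appendix 2, item 19.** The pooled groupings are optional, and every one uses PTM pooled over Parts A, B and C. The ANCOVA code contains treatment and baseline and nothing else.

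For all-cause MAV or death, SAP 6.2.1 has the groups "compared among 3 treatment groups in Part A and Part B and between the 2 treatment groups in Part C using a log-rank test", and the COVID-19-related composite follows the same method. Protocol 8.5.2 has these proportions "estimated using Kaplan-Meier methods by treatment group in Part C" and names no test.

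**The concern.** Parts A and B hold four of the five RDV regimens. On the primary endpoint they get arm summaries and no planned estimate of difference from their own placebo arm. The stated reason is small size. Small size is a reason to avoid a significance claim, but not to withhold a difference with its interval. In the same arms the plan does run log-rank tests on clinical events, and those tests go further than protocol 8.5.2.

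The within-Part contrast is the one that randomization protects. Without it, the only model-based figure for these doses is the pooled comparison, whose controls come mostly from other Parts. Otherwise readers will set arm means side by side, unadjusted for baseline viral load, although the SAP considers that covariate important enough to include in Part C.

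**Working it through.** **Planned sizes (protocol synopsis and 8.9).** 36 + 36 + 80 = 152, which reproduces the stated total. Allocation 1:1:1 gives 12 per arm in Parts A and B. Allocation 3:1 gives 60 and 20 in Part C. The documents give no SD, effect size, event rate or power calculation.

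**Precision of a within-Part ANCOVA.** Half-width in residual SD units = t(0.975, df) × √(1/n₁ + 1/n₂). Residual df is 36 − 3 arms − 1 slope = 32 in Part A or B, and 80 − 2 − 1 = 77 in Part C. Chance baseline imbalance between arms is ignored.

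| Contrast | √(1/n₁ + 1/n₂) | t | Half-width (SD) |
|---|---|---|---|
| One regimen v own PTM, 12 v 12 | 0.408 | 2.037 | 0.83 |
| Both durations v own PTM, 24 v 12 | 0.354 | 2.037 | 0.72 |
| Part C, 60 v 20 | 0.258 | 1.991 | 0.51 |

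Ratios to Part C are 0.83/0.51 ≈ 1.6 and 0.72/0.51 ≈ 1.4. If the residual SD is assumed to lie between 0.75 and 1.5 log10 copies/mL, the half-widths are 0.62 to 1.25, 0.54 to 1.08 and 0.39 to 0.77 log10.

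These are best case. The primary set for viral load is the mFAS (SAP 3.1.3), which drops baseline-negative participants separately by specimen. With an assumed 9 per arm, df = 27 − 4 = 23 and the 12 v 12 figure becomes 2.069 × √(2/9) = 0.98 SD.

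**What the pooled ANCOVA supplies instead.** Pooled PTM is 12 + 12 + 20 = 44. For either dose, 44 − 12 = 32 controls (73%) were randomized in another Part. With no Part term, if those controls differ by δ in DAVG7 after baseline adjustment, the estimate moves by about 0.73δ: 0.36 log10 for an assumed δ of 0.5, and 0.73 for δ of 1.0.

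A difference between Parts is plausible from the design alone, and a check on baseline characteristics would not reveal it:

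- Parts A and B use a sealed facemask and Part C a mouthpiece (protocol 5.3). The SBECD content of the formulations differs, 15% against 7.5% after reconstitution (protocol 1.3).
- Screening was sequential. The first Part B participant was screened on 29 October 2020 and the first Part C participant on 24 January 2021 (SAP Appendix 2, item 17).
- DAVG7 starts from the first postbaseline sample (SAP 6.1.1). That is nominally Day 2 in Parts A and B and Day 3 in Part C. For a steady fall of r log10 per day from Day 1, the average over Days 2 to 7 is (2 + 7)/2 − 1 = 3.5 days of decline. Over Days 3 to 7 it is (3 + 7)/2 − 1 = 4.0 days. Identical viral courses therefore give −3.5r and −4.0r.

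**Is small size applied evenly?** In the same arms of about 12, SAP 6.2.1 plans three-group log-rank tests on both MAV/death composites. It also plans log-rank tests on hospitalization and time to negative PCR with no restriction by Part. SAP 5.1 and 5.2 plan Kruskal-Wallis tests across three groups at baseline. DAVG7 is the endpoint for which small size is given as the reason for no comparison.

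**The case against.** The strongest defence is that SAP 6.1.3 follows the protocol body. Protocol 8.5.1 makes Parts A and B descriptive, the study has no power calculation, and its aim is to characterize viral load. Descriptive reporting at 12 per arm is a defensible choice. The synopsis does not say within Part and names no test or interval. The first pooled grouping in SAP 3.2, which sets each of the five regimens against pooled PTM, could be said to satisfy it. Most of this stands. What remains is that the synopsis and 8.5.1 do not say the same thing, and the pooled route is conditional, optional and mostly cross-Part.

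Three stronger readings are tempting, and the documents do not support them.

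- *That the SAP abandoned a protocol commitment.* The tension lies inside the protocol, between the synopsis and 8.5.1.
- *That the 31 mg and 62 mg groups have no randomized answer at all, or that a reader could not tell a null result from an imprecise one.* SAP Section 3 requires n, mean and SD or SE by randomized group, so an unadjusted within-Part difference and interval can be worked out by hand. What is missing is the pre-specified, baseline-adjusted one.
- *That the log-rank tests are run on rare events.* Neither document gives a MAV, death or hospitalization rate, and all-cause MAV covers any in-person visit with a health care professional. Rarity would be an assumption: at an assumed 5% rate a 36-person Part expects 36 × 0.05 = 1.8 events, and at assumed rates of 10%, 10% and 30% it expects 12 × 0.5 = 6.0.

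**Conclusion.** The point holds in this form: no baseline-adjusted within-Part difference with an interval is planned on the primary endpoint for the 31 mg and 62 mg regimens. The small-sample reason given does not fit the log-rank tests kept in the same Parts, and those MAV/death analyses exceed protocol 8.5.2. The pooled ANCOVA does not fill the gap, since 73% of its controls for either dose come from other Parts and the model has no Part term.

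The missing estimates would be imprecise, at about 1.6 times the Part C half-width for one regimen and 1.4 times for both durations combined. They would still show which effects the data cannot exclude. The figures rest on the planned arm sizes, no mFAS exclusions and a common residual SD within each Part. The log10 versions also rest on an assumed SD. This is a gain in reporting that should be made. It does not affect the Part C analysis.

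**What to change.** In SAP 6.1.3, replace the statement that no comparison is applied in Parts A and B. For each specimen type, fit one three-arm ANCOVA (arm, baseline viral load) within Part A and one within Part B. Report the LS-mean difference and 95% CI for each RDV regimen, and for the two durations combined, against that Part's own PTM. Label these descriptive and give no p-value.

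Word the synopsis and protocol 8.5.1 to say the same. In SAP 6.2.1, make the Part A and B MAV/death analyses descriptive, in line with protocol 8.5.2.

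Cost: 2 Parts × 3 specimen types = 6 model runs with the code in SAP Appendix 2, item 19. That code gives pairwise differences only, so the combined-durations contrast needs an added statement. The output is 3 contrasts × 6 runs = 18 intervals, wide and unadjusted for multiplicity, and they must be labelled that way. This change does not repair the pooled model, where the missing Part term is a separate matter.
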